6.5 Indicators

6.5.1 Indicators of clinical cure rate

6.5.1.1 Subjective Symptoms Score

- Pain: according to the subjective feelings of subjects, a 3-score scale is used (0=none, 1=mild, 2=moderate, 3=severe)
- Sensation of foreign body: according to the subjective feelings of subjects, a 3-score scale is used (0=none, 1=mild, 2=moderate, 3=severe)
- Photophobia: according to the subjective feelings of subjects, a 3-score scale is used (0=none, 1=mild, 2=moderate, 3=severe)

- Weep: according to the subjective feelings of subjects, a 3-score scale is used (0=none, 1=mild, 2=moderate, 3=severe)

See Appendix 1: Symptom Scoring Criteria for specific scoring criteria.

6.5.1.2 Objective Clinical Score:

- Scores of conjunctival hyperemia: Score the conjunctival hyperemia of the palpebral conjunctiva and bulbar conjunctiva respectively, using a 3-point scale (0= none, 1= mild, 2= moderate, 3= severe) to score the conjunctival hyperemia;
- Scores of conjunctival secretions/exudation: A 3-point scale (0= none, 1= mild, 2= moderate, 3= severe) is used to score conjunctival secretions.
- Scores of conjunctival edema: A 3-point scale (0= none, 1= mild, 2= moderate, 3= severe) is used to score conjunctival edema.

6.5.2 Other Clinical Observation Indicators

Analysis of best-corrected visual acuity, slit-lamp examination, intraocular pressure measurement, fundus examination, corneal endothelial cell count.

6.5.3 Biological sample test indicators

Collection of conjunctival sac secretions: Collect a bacterial culture tube and sterile swab from the central laboratory before sampling, and fully expose the bulbar conjunctiva and fornical conjunctiva when sampling. Use a sterile swab moistened with sterile 0.9% sodium chloride solution to gently swab the surface of the conjunctival sac 4 times starting from the inner canthus and rotating from the inside to the outside (pay attention not to missing the inner canthus, and collect the dense secretions), avoid contact with the eyelashes and eyelid margins, and use eyelid speculum and other appliances if necessary. After sampling, put the specimens into a sterile transfer tube, mark them, and send them to the laboratory department of the hospital for bacterial culture. All subjects are required to take secretions from both eyes separately for bacterial culture, with the subject number and eye type indicated.

6.5.4 Laboratory test indicators

Serum Pregnancy (female).

6.5.5 Adverse Events

Any abnormal symptoms, signs, laboratory tests or other special tests that occur during the clinical study, that are normal before treatment and abnormal clinically significant after treatment or abnormal clinically significant before treatment and worsen after treatment, regardless of its severity and whether it is related to the drug, should be recorded in detail, including the time of occurrence, clinical manifestation, severity (graded according to Common Terminology Criteria for Adverse Events (CTCAE) 5.0), management process, results and the degree of correlation with the study drug (definitely related, probably related, possibly related, possibly unrelated, definitely unrelated), and followed up until return to normal or baseline level or the investigator can give a reasonable explanation for the abnormality and believes that follow-up is not necessary. Those that are definitely related, probably related, possibly related are classified as adverse reactions.

In this study, the following abnormal laboratory values that were considered clinically significant were not treated as adverse events:

Abnormal laboratory test values with clinical significance that existed before enrollment, for example, the subject may have other systemic diseases, but no significant clinically significant changes occurred during the study will not be considered adverse events.

7. Assessment of Efficacy

7.1 Clinical Efficacy Assessment

Clinical cure rate: The proportion of subjects with a score of 0 (on a 3-point scale) for bulbar conjunctival congestion and 0 (on a 3-point scale) for conjunctival secretion/exudation at Visit 4/End of Treatment (EOT) (Day 8±1 day) and Visit 5/End of Study (EOS) (Day 14±1 day).

Clinical improvement rate = (pre-treatment score - post-treatment score) / pre-treatment score x 100%. The score of symptoms and signs is the sum of the scores for pain, foreign body sensation, photophobia, tearing, conjunctival congestion, conjunctival secretion/exudation and conjunctival edema.

Total effective rate (%) = (number of subjects cured+ number of subjects markedly effective) / total number of subjects available for evaluation of efficacy x 100%. Comprehensive efficacy evaluation: defined as cured, markedly effective, effective and ineffective; Calculate the total effective rate; See Appendix 2: Evaluation criteria of comprehensive efficacy for judgment criteria.

7.2 Biological Sample Test Indicators

7.2.1 Bacterial clearance rate

Bacterial clearance is defined as positive bacterial culture at baseline and negative bacterial culture at the last visit.

Bacterial clearance rate = (number of subjects cleared + number of subjects assumed to be cleared) / total number of subjects enrolled x 100%.

For the clearance rate of each major pathogenic bacteria, stratified analysis shall be conducted according to the type of pathogenic bacteria and the visit time point, and the clearance rate of each kind of bacteria by the investigational drug at different times shall be calculated.

The specific judgment criteria are as follows:

Clearance: No pathogenic bacteria of the original infection are cultured in the specimen culture from the original infection site after treatment;

Assumed clearance: Bacteriological results are considered assumed clearance in certain diseases where the disappearance of signs and symptoms makes culturable materials unavailable or the method of obtaining specimens is too invasive for recovered patients;

Not cleared: The pathogenic bacteria of the original infection are still cultured in the specimen culture from the original infection site after treatment;

Assumed not cleared: For patients judged to be clinically ineffective, if the culture has not been done or is unlikely to be done, the pathogenic bacteria can be assumed not cleared;

Partial clearance: At least one of the multiple pathogenic bacteria isolated at the original infection site is cleared at the end of treatment;

Replaced: Those whose bacterial culture results 1 week after treatment show negative results for the original pathogen bacteria and the appearance of new pathogen bacteria, but with no relevant symptoms and signs observed;

Re-infected: Those whose bacterial culture results 1 week after treatment show negative results for the original pathogen bacteria, but with new pathogenic bacteria appearing and signs and symptoms related to re-infection.

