1.1 Background

Acute conjunctivitis (also known as "pink eye") is the most common and contagious ocular infection in the United States, Asia and Europe and is a major cause of ocular morbidity, epidemic eye infections, loss of productivity and discomfort in patients. The primary causes are bacterial (mainly gram-positive and gram-negative), fungal, and viral (mainly adenovirus) infections^[1]. Acute bacterial conjunctivitis can occur in people of different ages, genders, regions, and social strata.

The main clinical manifestations of acute bacterial conjunctivitis are eyelid swelling, conjunctival congestion and purulent secretions on the conjunctival surface. The secretions are mucous at first and then purulent. Acute bacterial conjunctivitis usually does not cause permanent vision loss and eye structure damage, and has obvious self-limiting properties. Even without treatment, it can be cured within 10 to 14 days.

At present, acute bacterial conjunctivitis is mainly treated with topical antibiotics and broad-spectrum antibiotics. However, due to irrational use of antibiotics in clinical practice, some pathogenic bacteria develop resistance to related antibiotics. Under such circumstances, treatment with antibiotics cannot achieve the desired therapeutic effect, and the best timing for treatment will be missed, thereby indirectly increasing the medical burden of patients.

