7.2.2 Evaluation of specific etiological efficacy

(1) Bacterial culture positivity rate = the number of positive bacterial culture as a percentage of the total number of cases in the study.

(2) Bacterial species clearance rate = the total number of bacterial species cleared as a percentage of the total number of pathogenic species isolated at the end of treatment.

(3) Negative conversion rate of bacterial culture = The percentage of patients whose bacterial culture turns negative after treatment among those with positive bacterial culture before treatment.

(4) Stratified evaluation of pathogens

① Analysis of 120 patients at the end of all studies

Pathogen/Number of patients	Cleared	Not cleared	Replaced	Re-infected
Staphylococcus aureus				
Streptococcus pneumoniae				
Haemophilus influenza				
Corynebacterium				
Streptococcus hemolyticus				

② Observation of different pathogens for different duration of administration

Duration of administration / Number of patients	Staphylococcus aureus	Streptococcus pneumoniae	Haemophilus influenza	Corynebacterium	Streptococcus hemolyticus
Baseline					
Visit 2					
Visit 3					
Visit 4					
Visit 5					

8. Compliance

Compliance will be determined by subject self-report as recorded in subject diaries. Missing diary data may be collected by subject questioning. There will also be drug dispensing and return logs to be completed by the investigative site.

% = actual number of medication times / theoretical number of medication times × 100%.

A calculated result less than 80% or greater than 120% was considered to be poor compliance

9. Assessment of Safety

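### Bacterial clearance is defined in two incompatible ways, and the plan does not say whether subjects who lose the original pathogen but grow a new one count as cleared

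*Combined protocol and SAP*

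**What the plan says.** Clearance of each major pathogen at Visits 2, 3, 4 and 5 is the only secondary endpoint in 2.2.2. The synopsis, 2.2.2 and 7.2.1 share one headline rule: "Bacterial clearance is defined as positive bacterial culture at baseline and negative bacterial culture at the last visit". The rate is cleared plus assumed-cleared subjects over all subjects enrolled.

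Section 7.2.1 then lists judgment criteria:

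- "Clearance: No pathogenic bacteria of the original infection are cultured in the specimen culture from the original infection site after treatment".
- "Not cleared: The pathogenic bacteria of the original infection are still cultured in the specimen culture from the original infection site after treatment".
- Replaced: cultures taken one week after treatment "show negative results for the original pathogen bacteria and the appearance of new pathogen bacteria", provided no relevant symptoms or signs are seen.
- Re-infected: the original pathogen is likewise negative, "but with new pathogenic bacteria appearing and signs and symptoms related to re-infection".

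The end-of-study table in 7.2.2 has separate columns for Cleared, Not cleared, Replaced and Re-infected.

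Two other measures in 7.2.2 matter here. Item (3) is a negative conversion rate for the culture as a whole, among baseline-positive patients. Item (2) is a species clearance rate, given as "the total number of bacterial species cleared as a percentage of the total number of pathogenic species isolated at the end of treatment".

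**The concern.** The headline rule concerns the whole culture, whereas the Clearance criterion concerns one organism. They part company for a subject whose original pathogen has gone but who grows something else. The plan foresees such subjects, since it has two classes for them, but it gives no order of precedence and does not say whether they enter the numerator.

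Read literally, the headline rule also defeats a rate stratified by pathogen: *S. aureus* would be scored as not eliminated because a different species grew. The endpoint could therefore be computed in two ways from the same cultures, and the choice could be made after the data are seen. Section 10.3.4 does not help. It names fungal clearance among the secondary indicators and gives no rule for bacteria.

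**Working it through.** The documents state no clearance rate, so there is no figure to reproduce. The check applies each rule to one subject and then counts.

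**1. One subject.** Baseline culture positive; at Visit 5 the original pathogen is absent and a new one grows.

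- Headline rule: not met, because the culture is not negative.
- Clearance criterion: met, because the original pathogen is absent.
- Not cleared criterion: not met, because it needs the original pathogen to persist.
- Replaced or Re-infected: met, depending on signs and symptoms.

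**2. Numerators.** Let N be the number enrolled in an arm (60, section 3.4), G the number who lose the original pathogen, and R those among G who grow a new one. Assumed-cleared subjects are the same under every rule and are left out.

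- Headline rule: (G − R)/N.
- Columns of 7.2.2 read as exclusive, counting Cleared only: (G − R)/N.
- Clearance criterion: G/N.

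There are thus two candidate values, and they differ by R/N.

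**3. Size, with assumed counts.** Take G = 36, pooled over pathogens. The Clearance criterion gives 36/60 = 60.0%. The other value is:

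- R = 2: 34/60 = 56.7%, a gap of 3.3 points.
- R = 6: 30/60 = 50.0%, a gap of 10.0 points.
- R = 10: 26/60 = 43.3%, a gap of 16.7 points.

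A second set of assumptions has 40% to 100% of an arm culture-positive, about 90% of these losing the original pathogen, and 5% to 20% of those growing a new organism. The low end is 22/60 = 36.7% against 21/60 = 35.0%, a gap of 1.7 points. The high end is 54/60 = 90.0% against 43/60 = 71.7%, a gap of 18.3 points. If R = 0 the rules agree.

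For the comparison of arms, the difference moves by (R1 − R2)/60. It shifts only if new growth is more common in one arm.

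**4. Timing.** The last dosing day is Day 7 (5.4) and Visit 5 is Day 14 ± 1, so Visit 5 falls 6 to 8 days after Day 7. The one-week timing in the Replaced and Re-infected criteria most naturally means Visit 5. On that reading these classes do not apply at Visits 2 to 4, but the conflict between the first two rules can still arise there.

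**5. Species rate, 7.2.2(2), a separate matter.** Let b be baseline species occurrences, c those cleared, and n new ones. The literal denominator is what grows at the end of treatment, (b − c) + n, so the rate is c/((b − c) + n). With assumed counts pooled over subjects of b = 50, c = 45, n = 0, this is 45/5 = 900%, where a baseline denominator gives 45/50 = 90%. If everything clears and nothing new grows, the denominator is zero.

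**6. Visit 5 culture.** The flow chart schedules secretion collection at Visit 5. The Visit 5 procedure list in 6.4 omits it.

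**The case against.** The strongest defence is that the criteria are introduced as the specific way to judge clearance, so they put the headline rule into operation and negative means negative for the original pathogen. The separate negative conversion rate in 7.2.2(3) supports this, because whole-culture negativity already has its own measure. The reading is plausible, but the text does not say so. It would also leave Replaced and Re-infected subjects meeting the Clearance criterion while sitting in other columns.

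It is also fair that this is an exploratory trial with no sample-size calculation (3.4), that the endpoint is secondary, and that analysts work on groups X and Y (3.5). The masked labels limit a choice that favours one arm, but they do not fix the rule in advance.

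For the species rate, the reference to the end of treatment may qualify the whole assessment and not just the isolates counted. That would remove the absurd values, but the sentence does not make it clear. This rate is not a declared endpoint.

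Four stronger readings are tempting and are not supported:

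- That the subject is formally Not cleared. That class requires the original pathogen to persist, so the subject only fails the headline rule.
- That there are three competing values. The headline rule and the exclusive columns give the same numerator.
- That the swing is 5 to 25 points. Dividing by an assumed 40 culture-positive subjects gives 36/40 = 90% against 85%, 75% or 65%, but the plan divides by subjects enrolled.
- That new acquisition by Visit 5 is expected and unrelated to the drug. Section 1.1 says only that acute conjunctivitis "is the most common and contagious ocular infection" in the regions it lists. It gives no rate of new growth and says nothing about its cause.

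**Conclusion.** The contradiction is in the current text and nothing in the combined document resolves it. The secondary endpoint has two possible values whenever at least one subject loses the original pathogen and grows another. The gap is R/60 per arm: 3.3 to 16.7 points with the main assumed counts, and 1.7 to 18.3 under the second set. These figures show scale only, because the documents give neither a culture-positive rate nor a new-organism rate. No effect on the comparison between arms has been shown.

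The species-rate denominator is a distinct wording fault. Taken literally, it can give a rate above 100% or none at all. Both should be corrected. Neither touches the primary endpoint.

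**What to change.** - For the pathogen-stratified rate in the synopsis, 2.2.2 and 7.2.1, define clearance at each visit as absence of the baseline pathogen from that visit's culture, in line with the existing Clearance criterion. Keep whole-culture negativity for the negative conversion rate in 7.2.2(3).
- State before the first unblinding that Replaced and Re-infected subjects count as cleared of the original pathogen, and show them as separate sub-classes in the 7.2.2 table. Keeping them as exclusive columns outside the numerator would also be coherent, but it sits less well with a per-pathogen rate. Either way the rule must be written down.
- In 7.2.2(2), make the denominator the pathogenic species isolated at baseline.
- Reconcile the flow chart with 6.4 on the Visit 5 swab, since the endpoint is declared at that visit.

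The cost is protocol and SAP wording, using cultures the flow chart already schedules. The downside is that a subject with a new infection can count as cleared, so new infections must be reported separately to stay visible.

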2.2.2 Secondary Endpoints

Clearance rate: The clearance rate of each major pathogenic bacteria at Visit 2, 3, 4 and 5: Stratified analysis shall be conducted according to the type of pathogenic bacteria and the visit time point, and the clearance rate of each kind of bacteria by the investigational drug at different times shall be calculated. Bacterial clearance is defined as positive bacterial culture at baseline and negative bacterial culture at the last visit. Bacterial clearance rate = (number of subjects cleared + number of subjects assumed to be cleared) / total number of subjects enrolled × 100%.

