3.1 Overall Design

A multi-center, randomized, parallel, positive drug-controlled study design is used. In this study, the test drug IVIEW-1201(1.0% povidone-iodine ophthalmic gel sterile solution) is selected for the test group and the positive control drug Ofloxacin Eye Drops is selected for the control group. There are a total of 120 subjects: 60 in the test group and 60 in the control group.

The subject population in this study are those aged 15 and above (inclusive) with a confirmed diagnosis of acute bacterial conjunctivitis. Subjects should complete the random allocation and initial administration of the investigational drug on the day of diagnosis.

This study will be divided into 5 visit phases, namely Visit 1 (screening/baseline period, Day 1), Visit 2 (Day 3), Visit 3 (Day 6), Visit 4/End of Treatment(EOT) (Day 8 ±1 day) and Visit 5/End of Study(EOS) (Day 14±1 day).

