4.1 Inclusion Criteria

Inclusion Criteria:

Potential study subjects must meet **all** of the following inclusion criteria to be enrolled in this study.

1. Volunteered to participate in the study and signed the Informed Consent Form after receiving a verbal and written explanation of this clinical trial. In cases where the subject is unable to sign the Informed Consent Form, his/her guardian may sign in accordance with relevant regulations.
2. Aged above 15 (inclusive), male or female.
3. A diagnosis of acute bacterial conjunctivitis based on clinical observations: a) a score of ≥ 1 for bulbar conjunctival congestion and ≥ 1 for conjunctival secretion/exudation in at least one eye (same eye); and b) increased purulent, mucopurulent or mucopurulent secretions are observed in the conjunctival sac of the affected eye in all patients.
4. Willing to cooperate in the completion of all procedures and visits required for the trial.

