10.3 Statistical Analysis

10.3.1 Selection of statistical analysis data set

- 1) Full Analysis Set (FAS): All subjects randomized and for whom the data of at least one post-dose efficacy indicator is collected. Only the following randomized subjects are excluded: Subjects who violates key eligibility criteria, who are not treated with the investigational drug, and who have no observed data after randomization.
- 2) Per Protocol Set (PPS): A subset of the FAS, excluding subjects with significant protocol violations that may affect the primary efficacy evaluation based on the FAS.
- 3) Safety Set (SS): All subjects who have used the study drug at least once.

The efficacy analysis is mainly based on the FAS, but also on the PPS; the SS is used for safety analysis.

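### The bacterial clearance rate counts only baseline-positive subjects as cleared but divides by everyone enrolled, so on its own definition it understates clearance

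*Combined protocol and SAP*

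**What the plan says.** The only secondary endpoint listed in the synopsis and in 2.2.2 is bacterial clearance, reported as "The clearance rate of each major pathogenic bacteria at Visit 2, 3, 4 and 5". Section 7.2.1 repeats it and gives the judgment criteria.

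- **Definition (7.2.1):** "Bacterial clearance is defined as positive bacterial culture at baseline and negative bacterial culture at the last visit".
- **Formula (7.2.1, same in the synopsis and 2.2.2):** "Bacterial clearance rate = (number of subjects cleared + number of subjects assumed to be cleared) / total number of subjects enrolled".
- **Assumed clearance (7.2.1):** applies where, among other reasons, "the disappearance of signs and symptoms makes culturable materials unavailable". The sentence does not repeat the requirement of a positive baseline culture.
- **Entry (4.1):** "A diagnosis of acute bacterial conjunctivitis based on clinical observations".
- **Timing (3.1):** "Subjects should complete the random allocation and initial administration of the investigational drug on the day of diagnosis".
- **Analysis sets (10.3.1):** the FAS has no culture condition. The PPS is a subset of it, "excluding subjects with significant protocol violations that may affect the primary efficacy evaluation based on the FAS". A negative culture breaches no criterion, so it is not a protocol violation.
- **Related outputs (7.2.2):** item (1) is "Bacterial culture positivity rate = the number of positive bacterial culture as a percentage of the total number of cases in the study". Item (3) is a negative conversion rate whose denominator is patients positive before treatment.

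**The concern.** Numerator and denominator describe different populations. Under the stated definition a baseline-negative subject cannot be cleared, but still counts in the denominator. The plan does not assume that everyone is positive, because 7.2.2(1) sets out to measure positivity.

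Three things follow if the formula is applied as written. The rate is not a clearance rate, since its maximum is the baseline positivity and not 100%. It moves with chance differences in positivity between arms, which have nothing to do with treatment. It is also less sensitive to a real difference in clearance. The trial is meant to inform Phase III, and a reader who takes the named endpoint at face value would carry a diluted figure forward.

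Two wording gaps add to this. Clearance is judged at the last visit, yet the rate is reported at Visits 2 to 5. No separate denominator is given for each pathogen, although that is how the endpoint is to be reported.

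**Working it through.** The documents give no expected clearance or positivity and no power for this endpoint, and 3.4 states that the sample size was not calculated statistically. There is no plan figure to reproduce.

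**Inputs.** From the documents: 60 subjects per arm (3.1) and a chi-square or Fisher test for categorical indicators (10.3.2). Assumed: baseline positivity *p* of 40-70%, and clearance among positives *c* of 90%, 80% or 70%.

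**1. What the formula returns.** With baseline-negative subjects never cleared, reported rate = (60 × *p* × *c*) / 60 = *p* × *c*. With positives as denominator it is *c*.

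- *p* = 40%, *c* = 90%: 0.40 × 0.90 = 36%
- *p* = 50%, *c* = 90%: 27/60 = 45%, against 27/30 = 90%
- *p* = 70%, *c* = 90%: 0.70 × 0.90 = 63%

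For a single pathogen, applying the formula literally to an assumed 9 cleared out of 10 carriers gives 9/60 = 15%, against 9/10 = 90%.

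**2. Imbalance between arms.** The SD of the between-arm difference in positivity is √(2*p*(1−*p*)/60), or 8.4 to 9.1 points. The exact chance of a difference of 10 points or more (at least 6 subjects) is 27-32%. At equal 90% clearance, a 10-point gap gives a false difference of 0.10 × 0.90 = 9 points.

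**3. Power and size.** Exact enumeration of the two-sided 5% Pearson chi-square test. Enrolled denominator: n = 60 per arm, rates *p*·*c*₁ and *p*·*c*₂. Positives: n = 60*p* per arm, rates *c*₁ and *c*₂.

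| *p* | 90% v 70%, enrolled | 90% v 70%, positives | 90% v 80%, enrolled | 90% v 80%, positives |
|---|---|---|---|---|
| 40% | 16% | 43% | 8% | 17% |
| 50% | 20% | 50% | 9% | 19% |
| 60% | 27% | 58% | 11% | 23% |
| 70% | 35% | 66% | 12% | 26% |

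For 90% against 70%, the gap narrows as positivity rises: 45% v 72% at *p* = 80%, 61% v 76% at 90%, and 80% for both at 100%. Letting the number of positives per arm vary at random gives 42-65% among positives at *p* = 40-70%. For 90% against 80%, neither denominator is informative. Test size at equal 90% clearance is 5.0-5.4% (enrolled) and 4.7-5.9% (positives, fixed numbers), so this is not a type I error problem.

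**4. If assumed clearance were applied to baseline-negative subjects.** Let *f* be the fraction of them so counted. The rate is then *p*·*c* + *f*(1−*p*). At *p* = 50% and *c* = 90%, *f* = 0, 50%, 90% and 100% give 45%, 70%, 90% and 95%. On that loose reading the direction of error is no longer fixed, and the rate can overstate.

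**The case against.** The strongest reply is that the plan already contains the undiluted figure. Section 7.2.2(3) is a conversion rate among baseline positives, 7.2.2(1) reports positivity, and the 7.2.2 tables count outcomes and patients by pathogen. No data are lost, and if positivity is reported at baseline by arm, the diluted rate can be converted back. This stands and limits the harm. But 2.2.2 does not point to those items, and the named endpoint keeps its formula.

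Stratifying by pathogen could also be read as making carriers of that pathogen the stratum, in which case the dilution need not reach the per-pathogen rates. The text does not say so, and the only formula given uses all enrolled. The point then rests on the pooled formula, with the per-pathogen denominator left ambiguous.

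The power figures rest on assumed inputs and on Pearson's test, while the plan also allows Fisher's test without saying when. If Fisher is used whenever an expected count is below 5 (an assumption), power among positives for 90% against 70% falls to 39%, 47%, 57% and 66% at 40%, 50%, 60% and 70% positivity. The enrolled figures hardly move. The gap shrinks slightly at low positivity, and the direction holds.

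Dividing by all enrolled might be defended as protecting randomisation. Baseline culture status is fixed before treatment, so restricting to positives keeps the randomised comparison.

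Finally, 10.3.4 defers other indicators to a Statistical Analysis Plan, and no separate text of one is among the documents. It might state a working denominator, but that would not correct the protocol's formula.

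**Conclusion.** The concern holds. On its stated definition, the pooled rate equals positivity times clearance and understates clearance whenever any enrolled subject is culture-negative at baseline. That result is algebraic. Its size depends on positivity, which the documents do not give. At an assumed 40-70%, true clearance of 90% appears as 36-63%, and power for 90% against 70% drops from 43-66% to 16-35%.

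This is lost sensitivity and a hard-to-read estimate in an exploratory trial. It is neither a missed power target nor an inflated error rate. It should be fixed, but it does not threaten the primary endpoint.

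**What to change.** In the synopsis, 2.2.2 and 7.2.1:

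- Replace the all-enrolled denominator with *FAS subjects with a positive baseline culture in an eye affected at Visit 1*. This follows the principle of 7.2.2(3), which names neither the FAS nor the eye. For each pathogen, use subjects with that pathogen at baseline.
- Require a positive baseline culture for assumed clearance.
- Judge clearance at the visit being assessed, not at the last visit, so that the definition fits reporting at Visits 2 to 5.

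Some details must be settled for the rate to be computable. State how a subject with two affected eyes is scored, since both eyes are cultured and 10.3.4 speaks of a target eye. Choose between a negative culture and absence of the original pathogen, which 7.2.1 uses side by side, and assign the partial, replaced and re-infected categories. Reconcile the secondary indicators in the synopsis statistics section and 10.3.4 (fungal clearance, change in visual acuity) with the endpoint in 2.2.2.

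The cost is mostly wording, because cultures at baseline and Visits 2 to 4 are already planned. The Visit 5 culture is in the flow chart but not in the 6.4 procedure list, and the two must be reconciled. A general rule for missing follow-up cultures is also needed, because 10.3.3 covers primary indicators only and 7.2.1 covers only certain unsampled cases. The price is a smaller denominator: about 24 to 42 per arm (60 × 0.40 to 60 × 0.70) instead of 60.
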